9.11.1. Statistical considerations for the primary study

Statistical analyses for the interim analysis will be performed on all the data collected and cleaned for the subjects recruited in the first year of the study, at the end of recruitment (expected after 18 months) or in June 2015 whichever occurs first.

The interim analysis will be purely descriptive, no adjustment of the type I error is foreseen.

9.11.2. Statistical considerations for the extension study

All statistical analyses pertaining to the *extension study* will be performed on data collected and cleaned for the subjects who re-consented for the extension.

An interim analysis for the extension study will be conducted near the midway point of extension study data collection, after all subjects have reached four years of age (and completed their annual contact, or passed the window for that contact). The interim analysis will be purely descriptive, no adjustment of the type I error is foreseen.

Final extension study analysis will be conducted after all subjects have reached six years of age (and completed their annual contact, or passed the window for that contact).

10. ADMINISTRATIVE MATTERS

To comply with ICH GCP or other applicable guidelines administrative obligations relating to data collection, monitoring, archiving data, audits, confidentiality, ownership and publications must be met.

10.1. Remote Data Entry instructions

Remote Data Entry (RDE), a validated computer application, will be used as the method for data collection.

In all cases, subject initials will not be collected nor transmitted to GSK. Subject data necessary for analysis and reporting will be entered/transmitted into a validated database or data system. Clinical data management will be performed in accordance with applicable GSK standards and data cleaning procedures.

While completed eCRFs are reviewed by a GSK Biologicals' Site Monitor at the study site, omissions or inconsistencies detected by subsequent eCRF review may necessitate clarification or correction of omissions or inconsistencies with documentation and approval by the investigator or appropriately qualified designee. In all cases, the investigator remains accountable for the study data.

Once the database is archived and the clinical study report is complete and approved by all parties, each participating investigator will be provided with a CD-ROM of the final version of the data generated at his/her investigational site.

10.2. Study monitoring by GSK Biologicals

GSK will monitor the study to verify that, amongst others, the:

- Data are authentic, accurate, and complete.
- Safety and rights of subjects are being protected.
- Study is conducted in accordance with the currently approved protocol, any other study agreements, GCP and all applicable regulatory requirements.

The investigator and the head of the medical institution (where applicable) agrees to allow the monitor direct access to all relevant documents.

The investigator must ensure provision of reasonable time, space and qualified personnel for monitoring visits.

Direct access to all study-site related and source data is mandatory for the purpose of monitoring review. The monitor will perform a RDE review and a Source Document Verification (SDV). By SDV we understand verifying RDE entries by comparing them with the source data that will be made available by the investigator for this purpose.

The Source Documentation Agreement Form describes the source data for the different data in the RDE. This document should be completed and signed by the site monitor and investigator and should be filed in the monitor's and investigator's study file. Any data item for which the RDE will serve as the source must be identified, agreed and documented in the source documentation agreement form.

For RDE, the monitor will mark completed and approved screens at each visit.

Upon completion or premature discontinuation of the study, the monitor will conduct site closure activities with the investigator or site staff, as appropriate, in accordance with applicable regulations, GCP, and GSK procedures.

10.3. Record retention

Following closure of the study, the investigator must maintain all site study records (except for those required by local regulations to be maintained elsewhere) in a safe and secure location. The records must be easily accessible, when needed (e.g., audit or inspection), and must be available for review in conjunction with assessment of the facility, supporting systems, and staff. Where permitted by applicable laws/regulations or institutional policy, some or all of these records can be maintained in a validated format other than hard copy (e.g., microfiche, scanned, electronic); however, caution needs to be exercised before such action is taken. The investigator must ensure that all reproductions are legible and are a true and accurate copy of the original and meet accessibility and retrieval standards, including re-generating a hard copy, if required. Furthermore, the investigator must ensure that an acceptable back-up of the reproductions exists and that there is an acceptable quality control procedure in place for making these reproductions.

GSK will inform the investigator/institution of the time period for retaining these records to comply with all applicable regulatory requirements. However, the investigator/institution should seek the written approval of the Sponsor before proceeding with the disposal of these records. The minimum retention time will meet the strictest standard applicable to a particular site, as dictated by ICH GCP or other applicable guidelines, any institutional requirements or applicable laws or regulations, or GSK standards/procedures; otherwise, the minimum retention period will default to 15 years.

The investigator/institution must notify GSK of any changes in the archival arrangements, including, but not limited to, archival at an off-site facility and transfer of ownership of the records in the event the investigator leaves the site.

10.4. Quality assurance

To ensure compliance with GCP or other applicable guidelines and all applicable regulatory requirements, GSK may conduct a quality assurance audit. Regulatory agencies may also conduct a regulatory inspection of this study. Such audits/inspections can occur at any time during or after completion of the study. If an audit or inspection occurs, the investigator and institution agree to allow the auditor/inspector direct access to all relevant documents and to allocate his/her time and the time of his/her staff to the auditor/inspector to discuss findings and any relevant issues.

10.5. Posting of information on publicly available registers and publication policy

Study information from this protocol will be posted on public registers before enrollment of subjects begins/before start of the analyses.

Interventional studies that do not evaluate vaccines/products are progressed for publication in the scientific literature when the results provide important scientific or medical knowledge.

10.6. Provision of study results to investigators

Where required by applicable regulatory requirements, an investigator signatory will be identified for the approval of the study report. The investigator will be provided reasonable access to statistical tables, figures, and relevant reports and will have the opportunity to review the complete study results at a GSK Biologicals site or other mutually-agreed location.

GSK Biologicals will also provide the investigator with the full summary of the study results. The investigator is encouraged to share the summary results with the study subjects, as appropriate.

11. COUNTRY SPECIFIC REQUIREMENTS

Not applicable.

APPENDIX A LABORATORY ASSAYS

Neutralization assay

The Serum Neutralization assay is a functional assay that measures the ability of serum antibodies to neutralise the cytopathic effects of RSV (for example, strains A and B) on the host cell line, hence RSV replication. In the first step of the assay, a specific quantity of a replication capable RSV virus and a defined dilution of serum are mixed and incubated. Each serum dilution is tested in duplicates. During the second step, the virus-serum reaction mixture is transferred on the host cells and only non-neutralized virus is able to infect and replicate in the host cells. This leads to the formation of a given number of plaque forming units (PFU) on the cell monolayer that can be detected using a fluorochrome-tagged anti-RSV antibody. The neutralising titer is determined by calculating the serum dilution inducing a 60% inhibition in PFUs compared to a cell monolayer infected with virus alone, without serum.

RT-qPCR assay

Briefly, RSV A and RSV B ribonucleic acids (RNAs) extracted from the nasal swabs are detected in a duplex PCR format using specific amplification primers and fluorescent probes designed in the RSV N gene, encoding the RSV nucleocapsid protein. The process involves nucleic acids extraction, conversion of RNA to complementary deoxyribonucleic acid (cDNA) by reverse transcription and detection by real- time PCR reaction using a calibration curve (absolute quantitation). The RSV viral load is reported as copies of RSV RNA per mL of sample.

хТАG^{тм} RVP Fast assay

xTAG[™] RVP Fast assay is a qualitative nucleic acid multiplex tests intended for the simultaneous detection and identification of multiple respiratory virus nucleic acids in nasal/nasopharyngeal swabs from individuals suspected of respiratory tract infections. A multiplexed PCR reaction is performed to amplify the regions of interest in the target human or infectious agent genes. The PCR reaction is treated to remove excess nucleotides and primers. The PCR reaction is then subjected to a primer extension step that is specific for the allele or the infectious agent that is being analyzed: Allele Specific Primer Extension (ASPE) or Target Specific Primer Extension (TSPE). The 5' end of the ASPE or TSPE primers is attached to an xTAG universal tag sequence. The 5' universal tag sequence is hybridized to the complementary anti-tag sequence coupled to a particular xMAP bead set. The hybridized beads are read by the xMAP system and results are analyzed by the data analysis software.

APPENDIX C OVERVIEW OF RECRUITMENT PLAN (PRIMARY STUDY) (AMENDED 15-DEC-2017)

- Subjects will be pre-selected to be enrolled in the study, by obtaining the informed consent from the parent(s)/LAR(s) during pregnancy, after 20 weeks of gestation and before the start of delivery, to include their child in the study at birth. On obtaining the consent, the subjects will be checked for inclusion and exclusion criteria applicable before birth. A pre-selected child not meeting the inclusion and exclusion and exclusion criteria will be considered a screening failure.
- On receiving consent, subject numbers will be assigned sequentially to each subject, according to the range of subject numbers allocated to each study center.
- After birth, the final inclusion and exclusion criteria will be checked and the informed consent will be updated with, time and date of birth and any other potentially relevant identifiers as applicable by local requirements and re-signed. Any pre-selected subject not meeting the eligibility criteria will be considered a screening failure.
- Subject recruitment is intended to occur over a period 18 months or until the planned target enrollment has been met. Assuming no delays in recruitment, two-thirds of the subjects (1600) will be recruited in Year 1 and the remaining one-third of the subjects (800) in the first half of Year 2 of the study. In case of any delays in recruitment for the first two-thirds of the subjects, the study duration will be extended until all these subjects have completed follow-up to 2 years of age. Delays in the recruitment of the last one-third of the subjects will be absorbed by a shorter follow-up period for these subjects, unless the decision is taken after the interim analysis to extend the study to allow all subjects to complete 2 years of follow-up.
- The recruitment will be performed using a first application of SBIR where subjects will be entered on obtaining ICF and recruitment is controlled on the monthly recruitment rate. The aim is to attain a reasonably stable number of subjects per month over the full recruitment period in order to achieve an equal spread in the age of subjects at first exposure to an RSV season. Recruitment will be actively controlled through the SBIR system on country level according to agreed targets, actual recruitment rates, and further recruitment potential, so as to achieve a sufficient population on a regional level. With concurrent recruitment across the globe (with different seasonality) and an intended, steady recruitment over 18 months, the following population is to be included;
 - Subjects from NH during first 6 months
 - Subjects from SH during first 6 months
 - Subjects from NH during second 6 months
 - Subjects from SH during second 6 months
 - Subjects from NH during third 6 months; repeat of first 6 months NH
 - Subjects from SH during third 6 months; repeat of first 6 months SH

 In case recruitment is extended beyond 18 months, subjects recruited in the fourth 6 month period are a repeat to those recruited during the second 6 month period

Figure 3 RSV seasons in Northern and Southern Hemispheres

NH=Northern hemisphere, SH=Southern Hemisphere. Figure assumes equal recruitment targets on both hemispheres (which is not a requirement for the study).

Figure A represents recruitment in the NH and assumes RSV seasons running from November to April relative to a currently estimated time point 0 in Nov 2013.

Figure B represents recruitment in the SH and assumed RSV seasons running from May to October relative to a currently estimated time point 0 in Nov 2013.

Recruitment on both Hemispheres will include a period of 'On Season' recruitment and a period of 'Off Season' recruitment and a third period of recruitment matching the first period.

An interim analysis data lock is scheduled after 1.5 years or in June 2015, whichever occurs first.

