5.1. Number of subjects/centres

Target enrollment for the primary study will be 2400 subjects to obtain approximately 1920 fully evaluable subjects at primary study completion. Target enrollment for extension period will be *a* maximum of 2400 subjects. (All subjects participating in the primary study whose parent(s)/LAR(s) give re-consent for the extension period and who fulfill all *relevant* inclusion/exclusion criteria *may be followed in the extension*.)

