- The risk factor analysis will be done using a Cox regression model and not a Poisson regression model to be consistent with the analysis performed in clinical trials.
- The sensitivity analysis will not be performed on the total enrolled cohort.
- The analysis of the impact of changes to the symptoms and threshold levels of symptoms in the LRTI case definition and severity scale will not be done by age category

200150 (EPI-RSV-005 BOD)

Statistical Analysis Plan Amendment 1 Final

- The date of study conclusion for subjects lost to follow-up will be the date of conclusion given in the CRF and will not be derived according to number of missed visits.
- Only first episode within a given age interval is considered for the computation of incidence. The incidence of event is computed using 3 different calculation methods: incidence rate, proportion affected, and incidence proportion. See section 11.1.1 for detail of calculation
- Sub-group of analysis for birth period outside or within transmission season will not be performed. Instead, the analysis will be based on the first 6 month of subject's life, and will be done considering 2 categories: <= 3 months and > 3 months. The incidence rate of RSV associate LRTI, severe LRTI, and hospitalization will be computed by country.
- Incidence and performance of case definition analysis (measures of agreement) will be performed using exploratory case definitions in anticipation of update to WHO case definitions.
- Analyses of cord blood collection using and not using recommended procedures will not be done. Instead, descriptive statistics for cord blood collection variables and cord blood levels of RSV A and B neutralizing antibodies according to cord blood collection variables will be provided. Additional analyses will be performed to evaluate disease surveillance and protocol procedures and include summary of number and percent of surveillance contacts followed by an exam visit, the duration between surveillance contact and exam visit, and duration between nasal swap and onset of symptoms.

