11.1.4. Computation of incidence proportion

Incidence proportion will be computed as the number of subjects had first episode in the age interval divided by the number of subject at risk of event at the beginning of the age interval. A subject that has an event will no longer consider of at risk, i.e. subjects with event in 0 - 1 month are excluded from denominator for future monthly incidence calculation. A 95% CI will be computed using an exact method.

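### Eighteen months of steady intake enrols some birth months more often than others, so by-country RSV incidence by month of age mixes the recruitment calendar with age; a standardised estimate beside it would separate the two

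*Protocol*

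**What the plan says.** Protocol Appendix C sets the intake: "Subject recruitment is intended to occur over a period 18 months or until the planned target enrollment has been met". Monthly numbers are to be held roughly constant "in order to achieve an equal spread in the age of subjects at first exposure to an RSV season". The planned blocks include "Subjects from NH during third 6 months; repeat of first 6 months NH", with a matching Southern entry. The notes to Figure 3 say that the Northern panel "assumes RSV seasons running from November to April relative to a currently estimated time point 0 in Nov 2013"; the Southern panel uses May to October. A fourth block, repeating the second, is mentioned only for the case that recruitment overruns 18 months. The rate is controlled when consent is obtained, and consent may be given at any time from 20 weeks of gestation to delivery.

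SAP 6.6.1 (Table 12) lists incidence proportion by monthly age among the analyses for the primary objectives, and Template 11 tabulates it by country for the first six months of life. SAP 11.1.4 gives this definition: "number of subjects had first episode in the age interval divided by the number of subject at risk of event at the beginning" (meaning the start of each monthly band), with no weight for birth month. The same section plans Kaplan-Meier curves and first-episode rates for 0-5 and 6-11 months, also by country. SAP section 9 states: "Sub-group of analysis for birth period outside or within transmission season will not be performed". It puts in place a split at three months of in-season follow-up during the first six months of life (Template 12).

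**The concern.** A child's chance of meeting RSV at a given month of age depends on which calendar months that month of age falls in. If every birth month is enrolled equally often, each month of age is in season for half the children and the age profile can be read as an age effect. An 18-month intake enrols six consecutive calendar months twice. The in-season share then changes with age in a way fixed by the recruitment calendar. Because the seasons are opposite, it changes in opposite directions in the two hemispheres.

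The rationale names maternal and pediatric vaccines as the use of these results, and the timing of risk within the first half-year is what a month-of-age table informs. A reader who sets Finland beside Argentina could take a calendar effect for epidemiology.

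**Working it through.** **Inputs.** 18-month steady intake, 2400 children, time 0 in November, and seasons November-April (North) and May-October (South), all from Appendix C. Temperate countries from SAP Table 10: Canada, United States, Finland, Argentina, South Africa.

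**The plan's own figure.** 2400 × 12/18 = 1600 in Year 1 and 2400 × 6/18 = 800 in the next half-year, as Appendix C states. So the plan does assume even monthly accrual.

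**Birth months.** If birth follows recruitment at once, November-April is enrolled twice and May-October once: 1600 against 800, or 67% against 33%. A 12- or 24-month intake would give 1200 against 1200.

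**In-season share by age.** For age *a* in months (under 6) and lag *l* from recruitment to birth (0 to 4), the Northern share in season is (6 + |*a* + *l* − 6|)/18. The Southern share is one minus this. The even-birth-year value is 1/2 at every age.

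- *No lag.* The share is (12 − *a*)/18. Over month 0 it averages 11.5/18 = 0.639, and 0.639/0.5 = 1.28. Over month 5 it averages 6.5/18 = 0.361, a ratio of 0.72. North over South is 11.5/6.5 = 1.77 at month 0 and 6.5/11.5 = 0.57 at month 5.
- *Lag uniform on 0-4 months (assumption).* November-April births are (12 − 2)/18 = 56%. Month 0: (12 − 2.5)/18 = 0.528, ratio 1.06. Month 3: the mean of |*a* + *l* − 6| is 1.083, so 7.083/18 = 0.394, ratio 0.79; month 4 is the same. Over 0-5 months the mean is 1.889, so 7.889/18 = 0.438, ratio 0.88.

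Northern error against an even birth year, all risk in season (Southern figures have the opposite sign):

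| Month of age | 0 | 1 | 2 | 3 | 4 | 5 | 0-5 total |
|---|---|---|---|---|---|---|---|
| No lag | +28% | +17% | +6% | −6% | −17% | −28% | 0% |
| Lag 0-4 months | +6% | −6% | −16% | −21% | −21% | −16% | −12% |

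The 6-11 month total mirrors the 0-5 total.

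**Off-season risk.** If off-season risk is a fraction *r* of in-season risk, every error is multiplied by (1 − *r*)/(1 + *r*). At *r* = 1/5 this is 0.8/1.2 = 0.67, so the errors shrink by one third: ±28% becomes ±19%, ±21% becomes ±14%, ±12% becomes ±8%.

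**Start month.** Moving time 0 through all twelve months leaves a largest error of 28% (no lag) or 21% (lag 0-4) at some month of age in the first six. Only its place and sign change.

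**Totals.** The 0-5 figures assume level risk within those six months, and the 0-11 total balances exactly only if risk is level over the year. With the age contrasts in the protocol's hospitalisation table (Table 12) and the 0-4 month lag, the Northern 0-11 total would be low by 12.3% × (18.5 − 7.4)/(18.5 + 7.4) = 5% to 12.3% × (16.9 − 5.1)/(16.9 + 5.1) = 7%, if all risk is in season.

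**Precision.** Protocol 9.3 takes about 320 evaluable children per country and an LRTI rate eight times the hospitalisation rate. At 20 per 1000 that is 320 × 0.16/12 ≈ 4 RSV LRTI cases per monthly cell, with an exact interval of 0.27 to 2.6 times the estimate. At the top tabulated rate, 44.1 per 1000, it is about 9 cases (0.46 to 1.9 times).

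**The case against.** Several counter-arguments carry weight.

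- **Consent, not birth, is what is held steady.** Births trail consent by up to about 4.6 months, which blurs the doubled half-year. This stands. A reader might infer that Northern countries will show too much disease in the first three months, or that a North-South ratio of 1.77 at month 0 is to be expected. The documents do not support either: both need birth in the month of recruitment and an exact November start, and Appendix C calls that start an estimate. The lag moves the error and does not remove it.
- **The repeat is deliberate and disclosed.** It serves the secondary objective on between-year variability (recruitment Months 1-6 against 13-18). That justifies the design, but neither makes the equal-spread statement true nor adjusts Template 11.
- **The hemispheres offset each other.** With equal Northern and Southern numbers the pooled in-season share would be one half. Figure 3 says equal targets are not required, and Template 11 is by country.
- **Other outputs show birth season.** Template 4 gives the share born in season, Template 16 the calendar month of cases, Template 12 a season-exposure split, and the Cox models a birth-season term. None of these enters Template 11. SAP 6.1.4.5 also sets the Northern season as April-September and the Southern as October-March, the reverse of Appendix C, so Template 12 and the Cox term cannot be read until the two are reconciled.
- **Cells are sparse and no North-South contrast is planned.** This stands and limits the weight of the point. Sampling error in one country's monthly cell will exceed the bias.

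**Conclusion.** The concern holds as a cheap improvement. Within a temperate country, an 18-month steady intake with a repeated block does not give an equal spread of age at first season. The unweighted month-of-age incidence, the Kaplan-Meier curves before 12 months and possibly the 0-5 and 6-11 month figures carry the recruitment calendar, with opposite signs in the two hemispheres. The largest monthly error is 21% to 28% if all risk is in season, and about one third less if off-season risk is one fifth of in-season. Where it falls depends on the actual start date and consent-to-birth lag, which the documents do not give.

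A reader might also infer that the main incidence results are biased. The documents do not support that: the 0-11 month and later totals are essentially unaffected, apart from a few percent where risk falls steeply with age. So are Thailand, Bangladesh and Honduras, on the SAP's all-year season for them. The calculation assumes six-month seasons, even accrual and little depletion of the at-risk set.

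**What to change.** State in Appendix C that 18 months of intake does not give an equal spread by country. In SAP 6.6.1 and 11.1.4, for the five temperate countries, add an estimate standardised to an even birth year beside the unweighted results in Template 11, the Kaplan-Meier curves before 12 months, and the 0-5 and 6-11 month rates. Weight each child by the inverse of the observed number of enrolled births in that calendar month in that country. This needs no assumption about start date or lag; adjacent months may have to be merged where a country has few births. Replace the exact interval by a robust or bootstrap one for the weighted estimates, since the exact method does not apply to weighted counts.

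Birth dates are already recorded, so the cost is added columns. Effective sample size in the temperate countries falls by about 11% with no lag (12²/(6×9 + 6×18) = 144/162 = 0.889) and about 6% with the 0-4 month lag, so intervals widen slightly.
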